## I. Background and Rationale

Overactive bladder (OAB) is a common condition with a prevalence ranging from 5.9% to 16.9% in the United States and has been found to increase with age. OAB has a negative impact on health related quality of life (QoL), and OAB patients have more anxiety and depression than controls. Primary treatment for OAB include behavioral modifications, such as decreased caffeine intake and timed voiding, and pelvic floor physical therapy. Second line therapy includes anticholinergic medicine/beta-3 adrenoceptor agonists. Unfortunately, compliance and adherence to these medications decreases over time likely due to side effects and/or efficacy.

Per AUA/SUFU guidelines, PTNS is a third line recommendation for OAB along with onabotulinumtoxinA (BTX) injection and sacral neuromodulation. The overall objective success (defined as  $\geq 50\%$  decrease in urge or urge urinary incontinence (UI) and 25% reduction in daytime and/or nighttime frequency) of PTNS has been published and ranges from 60% to 71%.

In the single sham-controlled trial (SUMiT: n=220), Peters et al reported that 54.5% of PTNS subjects had moderately or markedly improved bladder symptoms on global response assessments (GRA) compared to 20.9% of sham subjects ( $p < 0.001$ ). PTNS subjects also had statistically significant improvements in frequency, nighttime voids, voids with moderate to severe urgency and UI episodes compared to sham. Furthermore, significant improvements in bladder symptoms on GRA and quality of life (QoL) as measured with the Overactive Bladder Questionnaire (OABq) were observed after 12 but not 6 treatments, providing support for a 12-week treatment course. In another randomized, placebo controlled trial, Finazzi et al showed 71% response rate in the PTNS group compared to 0% in the sham, placebo group.

Most PTNS studies use induction protocols of one 30-minute treatment a week for 12 weeks (1x12) that provides 6 hours of PTNS time. The SUMiT trial showed statistically significant separation of the treatment arm over the sham only after the 10 week mark, or after 5 hours of stimulation. [Personal communication with [name].] There is interest in speeding up treatment by providing more frequent treatments, providing a longer stimulation time, or both, to more rapidly reach the 6-hour stimulation mark. Finazzi-Agro et al reported a randomized, placebo controlled trial with 12, 30-minute PTNS sessions, 3 times a week with a 71% response rate. Yoong et al placed patients on a truncated 1x6 (one 30-minute treatment for 6 weeks) treatment induction course with a calculated positive response rate of 69.7% after induction. Because the 1x6 course (3 hours of stimulation total) yielded a shorter median time to return of symptoms of 3 weeks (interquartile range of 2), however, they have since concluded a 1x12 course is more cost effective. There is also early data from an implanted chronic tibial nerve stimulation lead study that shows a minimum of 8 hours of tibial nerve stimulation a day results in significant improvement in incontinence episodes per day at one week ([name], personal communication, abstract submitted to SUFU).

Overactive bladder is a prevalent condition affecting up to one of every 6 adults. Because PTNS is a minimally invasive option there is much interest in increasing its overall use. Our study will test the concept of whether the PTNS effect is dose (total time of treatment) sensitive, and whether expanding the dosage of each treatment, i.e. from 30 minutes to 2 hours, will provide significant clinical improvement after a one week induction course.

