## III. Methodology

The aim of this study is to determine the efficacy of an accelerated course for percutaneous tibial nerve stimulation (PTNS) induction. The standard 12 weekly induction treatments may be a patient burden and a more rapid induction may speed up symptomatic improvement.

We anticipate enrolling 64 patients, in this randomized trial, 32 in each study arm. Patients will be recruited from Beaumont's Women's Urology Center, as well as private Urology offices. Eligible patients will be consented and randomized into 1 of 2 groups. Patients will be enrolled in the study and randomized:

- After all screening activities have occurred and it has been determined that the patient meets all inclusion criteria without the presence of exclusionary criteria.
- After the patient agrees to enroll and comply with the study protocol, regardless of study group assignment.

Patients will be randomized 1:1 to active PTNS treatment or Sham treatment

The process of randomization will be as follows:

- Randomization will be performed using a table of random numbers. Randomization envelopes will be provided by the study's biostatistician. Randomization assignment will be to either active PTNS treatment or Sham treatment. The randomization envelopes will be securely stored in a locked cabinet. The Research Coordinator(s) will ultimately be responsible for maintaining the confidentiality and security of the randomization envelopes.
- The biostatistician will prepare more envelopes, if necessary.
- After the participant is randomized, staff will complete the ***Subject Enrollment and Randomization Log***. The log may be stored in the locked cabinet with the envelopes. Ultimately the log will be stored in the regulatory binder.

All patients who enroll will be seen and treated at the Beaumont Urology clinical research suite.

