Consented patients will complete the Overactive Bladder Questionnaire Short Form (OAB-q SF), 3-day voiding diary and enrollment questionnaire (demographics, medical history, concomitant medications, etc.) prior to study enrollment. A urinalysis via urine dipstick and pregnancy test (for women of child bearing potential) will be performed at screening. If the urinalysis is positive for leukocytes a urine culture will be sent. Patients with a positive urine culture may be treated per standard of care by the study physician. After treatment is completed, a repeat urine will be checked. If repeat urinalysis is negative, the subject will be allowed to complete the voiding diary and continue with study activities. The diary will be collected and reviewed at the first scheduled treatment visit (within 21 days from screening visit). If the patient meets the eligibility criteria, they will be randomized (1:1) into the sham or accelerated PTNS group.

Our goal is to have patients complete all three treatments within one week (7 days) but as there are always impedances (scheduling conflicts, illness, etc.) we will allow patients to complete all treatments within 2 weeks (14 days) if necessary. Patients will be allowed back-to-back treatments (i.e. two days in a row) if they should elect to do so. Adverse events and concomitant medications will be assessed at each treatment whether sham or active PTNS. GRA will be gathered at each visit beginning with the second induction treatment.

After completing the one-week induction consisting of three active or sham treatments, patients will receive a phone call three days ( $\pm$  1 day) after the last treatment to assess for any adverse events as well as remind them to start filling out their 3 day diary if they have not already begun to do so. This will also serve as a reminder phone call for their upcoming appointment.

One week post-induction ( $\pm$ 3 days), patients will return for an office visit. OAB-q SF, GRA and 3-day voiding diary will be collected. We will also assess for adverse events and concomitant medications at this visit. A blinding assessment questionnaire will be administered as well. A urinalysis will be completed.

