At 4, 8, and 12 weeks post-induction ( $\pm$  7 days), patients will return for follow-up appointments. Non-modified OAB-q SF, GRA and 3-day voiding diary will be collected and a urinalysis completed. Maintenance treatments (sham or active PTNS depending on treatment arm) will be given. Maintenance treatment will consist of a 30 minute treatment per standard of care. We will also assess for adverse events and concomitant medications at each of these visits.

After all study activities are complete, patients will be un-blinded at week 12 marking the end of the study. Those who were in the sham arm will be offered the opportunity to continue on to the open label phase of the study. Subjects in the open label phase will be offered the same accelerated treatments as those in the initial active PTNS treatment group. They will have up to 12 weeks to decide if they would like to continue on to the open label phase. This option will also be offered to those who had been previously randomized to the Sham group prior to the protocol amendment, even if they have completed their visit schedule. The follow up schedule will also be conducted in the same manner. Either of the groups can be offered re-induction per insurance requirements if they elect to do so with their

physician or can seek alternative treatments (BTX, sacral neuromodulation, etc.) per standard of care.

Our goal is to have patients complete all three open label treatments within one week (7 days) again, as there are always impedances (scheduling conflicts, illness, etc.) we will allow patients to complete all treatments within 2 weeks (14 days) if necessary. Patients will be allowed back-to-back treatments (i.e. two days in a row) if they should elect to do so. Adverse events and concomitant medications will be assessed at each treatment whether sham or active PTNS. GRA will be gathered at each visit beginning with the second induction treatment.

After completing the one-week open label induction consisting of three active treatments, patients will receive a phone call three days ( $\pm$  1 day) after the last treatment to assess for any adverse events as well as remind them to start filling out their 3 day diary if they have not already begun to do so. This will also serve as a reminder phone call for their upcoming appointment.

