#### **ACTIVE PTNS GROUP:**

Position: Patients will be placed in a comfortable position, sitting or supine. The treatment leg will be propped up comfortably on a foot rest but draped and out of view from the patient.

Needle: A 34-gauge needle electrode will be inserted at a 60-degree angle approximately 5 cm cephalad to the medial malleolus and slightly posterior to the tibia (Fig. 1a in the appendix).

Electrode Pads: A PTNS surface electrode will be placed on the ipsilateral calcaneus as well as 2 inactive sham surface electrodes, 1 under the little toe and 1 on the top of the foot. When the PTNS lead set is connected to the Urgent PC stimulator, a current level of 0.5 to 9 mA at 20 Hz was selected based on each patient's foot and plantar motor and sensory responses.

Duration: This treatment will be maintained 60 minutes. The patient will be given a brief break between sessions. To complete the 120-minute session, the same treatment will be performed on the patient's other foot for 60 minutes.

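### Does the plan promise a test of dose sensitivity that a single active regimen against sham cannot deliver?

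*Combined protocol and SAP*

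**What the plan says.** The last paragraph of section I (Background and Rationale) gives two ideas in one sentence. The first is "Our study will test the concept of whether the PTNS effect is dose (total time of treatment) sensitive". The second is "whether expanding the dosage of each treatment, i.e. from 30 minutes to 2 hours, will provide significant clinical improvement after a one week induction course". The same section describes the usual induction course as "one 30-minute treatment a week for 12 weeks (1x12) that provides 6 hours of PTNS time".

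Section III (Methodology) states the aim more narrowly: "The aim of this study is to determine the efficacy of an accelerated course for percutaneous tibial nerve stimulation (PTNS) induction". It then sets two arms: "Patients will be randomized 1:1 to active PTNS treatment or Sham treatment". Follow-up is timed from the end of a common induction course ("After completing the one-week induction consisting of three active or sham treatments"). The Active PTNS Group text gives 60 minutes on one foot and continues: "To complete the 120-minute session, the same treatment will be performed on the patient's other foot for 60 minutes". The Sham Group text sets the same session length. Later visits are alike too: "Maintenance treatment will consist of a 30 minute treatment per standard of care". The open-label phase offers former sham patients the same accelerated course.

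Section II (Objectives and Endpoints) and section VI (Data Analysis) list comparisons of sham with PTNS on GRA, the voiding diary and the OABq-SF, plus changes from baseline. Neither contains a dose objective, a dose model, a historical comparison or an equivalence test.

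**The concern.** A trial that says it will test dose sensitivity should let the dose vary. Here every active patient is assigned the same induction and the same maintenance, and the comparator receives none of the active treatment. A positive result would show that this regimen beats sham, and a negative one that it was not shown to. Neither says whether response rises with total time.

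The worry is about interpretation. A win over sham might be reported as proof of dose response, or as equivalence to 12 weekly sessions, and a null result might be read as evidence against dose sensitivity. A second worry is that two hours split over two legs could be counted as 6 hours in total or as 3 hours per leg, which would leave the dose itself uncertain by a factor of two.

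**Working it through.** **1. Dose contrasts in the design.** Inputs: the two-arm 1:1 allocation (section III), three induction sessions (section III), 120 minutes per session (Active PTNS Group), 30-minute maintenance and the same regimen in the open-label phase (section III).

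- Active dose levels: 1.
- Randomised contrasts between active dose levels: 1 - 1 = 0.

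GRA is collected from the second induction treatment onward, so there are several sham-versus-PTNS comparisons as active time accumulates. In a single fixed regimen, accumulated time moves together with visit number and elapsed days, so these comparisons do not separate a dose effect either. The first clause in section I cannot be answered as a dose-response question.

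**2. What the sample size is for.** Inputs from section VI: 58.3% and 21.9% responders, 5% significance, 80% power, pooled-variance Z test, 10% dropout. Two-sided testing is assumed, because the text does not give sidedness.

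- Mean proportion: (0.583 + 0.219)/2 = 0.401.
- n per arm = [1.960 x sqrt(2 x 0.401 x 0.599) + 0.842 x sqrt(0.583 x 0.417 + 0.219 x 0.781)]^2 / (0.583 - 0.219)^2.
- = (1.358 + 0.542)^2 / 0.1325 = 3.610 / 0.1325 = 27.2, rounded up to 28.
- With dropout: 28 / 0.90 = 31.1, rounded up to 32 per arm, 64 in total.

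This matches the plan's figure. The calculation uses a PTNS rate and a sham rate and nothing else, so no part of the sample size rests on a dose question.

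**3. How total time is counted.** Section I defines dose as total time of treatment.

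- Accelerated course: 3 sessions x 120 min = 360 min = 6 h.
- Standard course: 12 sessions x 30 min = 360 min = 6 h.

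The two agree with each other and with section I, which speaks of reaching the 6-hour mark sooner. The alternative, 3 x 60 min = 3 h per leg, uses a measure that appears nowhere in the documents. No two places in the plan conflict.

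**4. Where the clause leads.**

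| Place | Question stated |
|---|---|
| Section I, first clause | Is the effect sensitive to total time? |
| Section I, second clause | Do 2-hour sessions give improvement after one week? |
| Section II | PTNS versus sham on GRA at one week |
| Section III | Efficacy of an accelerated course |
| Section VI | PTNS versus sham on GRA; sample size for the same |

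Only the first row is out of reach. The second can be tested against sham. It cannot be tested as 2 hours against 30 minutes, and no such comparison is planned.

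**The case for a change.** The strongest case for a change is that the sentence says what this study will test, defines dose explicitly, and joins the two ideas with a conjunction, so dose sensitivity stands as a question in its own right. The protocol then states its purpose in two different ways, and a reader who starts at section I may expect an answer that the data cannot give. A historical comparison would not supply it: by the plan's own count, the accelerated and standard courses both total 6 hours, so such a comparison would vary schedule and session length but not total time. All of this stands as a criticism of the wording.

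The per-leg count also has some force. Section I reports that the earlier sham-controlled trial separated from sham only after 5 hours, and that a 3-hour course was followed by earlier return of symptoms. Six hours lies above that 5-hour mark and three hours below it. This is a fair scientific question about how stimulation of two legs adds up. It concerns why the regimen might work, though, and the comparison with sham is valid whichever count is used.

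The feared misreadings are not in the plan. It proposes no dose-response conclusion, equivalence claim or historical analysis, so a disclaimer would rule out claims nobody has made. The context also allows a milder reading of the first clause: the background asks whether accumulated hours, rather than elapsed weeks, bring about the effect. Giving the usual 6 hours in about a week and comparing with sham is an indirect proof of concept for that idea.

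**Conclusion.** The observation is correct but calls for no change. With one active dose level and no randomised dose contrast, the trial can show whether the accelerated course beats sham, and cannot show how response varies with total time. One clause in section I overstates this. The aim in section III, the primary endpoint in section II and the analysis in section VI already pose the answerable question, and the 64 patients are sized for it.

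The effect of the slip on the trial is nil: no endpoint, test, sample size, visit or treatment depends on the clause, and rewording it would reproduce what sections II and III already say. The supposed two-fold uncertainty in dose falls away, because the plan's own definition gives 6 hours.

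This rests on two assumptions: that the analysis follows sections II and VI as written, and that the results are reported as a comparison with sham. If the sponsor later wished to claim a dose response or equivalence to the 12-week course, this trial would not support it, and the objection would then apply to that claim.

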## II. Objectives and Endpoints

- a. The primary endpoint will be assessed comparing GRA responses between sham and PTNS groups at one week ( $\pm$  3 days) post induction. This comparison will also be made for all other visits using t-tests or chi-square tests, as appropriate.
- b. Secondary endpoints will include comparisons between sham and PTNS groups looking at variables in the 3-day voiding diary and OABq-SF at one week ( $\pm$  3 days) post-induction. Voiding diary variables include frequency, nocturia, degree of urgency, and urge incontinent episodes. Changes from baseline will also be analyzed.

## III. Methodology

The aim of this study is to determine the efficacy of an accelerated course for percutaneous tibial nerve stimulation (PTNS) induction. The standard 12 weekly induction treatments may be a patient burden and a more rapid induction may speed up symptomatic improvement.

We anticipate enrolling 64 patients, in this randomized trial, 32 in each study arm. Patients will be recruited from Beaumont's Women's Urology Center, as well as private Urology offices. Eligible patients will be consented and randomized into 1 of 2 groups. Patients will be enrolled in the study and randomized:

- After all screening activities have occurred and it has been determined that the patient meets all inclusion criteria without the presence of exclusionary criteria.
- After the patient agrees to enroll and comply with the study protocol, regardless of study group assignment.

Patients will be randomized 1:1 to active PTNS treatment or Sham treatment

The process of randomization will be as follows:

- Randomization will be performed using a table of random numbers. Randomization envelopes will be provided by the study's biostatistician. Randomization assignment will be to either active PTNS treatment or Sham treatment. The randomization envelopes will be securely stored in a locked cabinet. The Research Coordinator(s) will ultimately be responsible for maintaining the confidentiality and security of the randomization envelopes.
- The biostatistician will prepare more envelopes, if necessary.
- After the participant is randomized, staff will complete the ***Subject Enrollment and Randomization Log***. The log may be stored in the locked cabinet with the envelopes. Ultimately the log will be stored in the regulatory binder.

All patients who enroll will be seen and treated at the Beaumont Urology clinical research suite.

Consented patients will complete the Overactive Bladder Questionnaire Short Form (OAB-q SF), 3-day voiding diary and enrollment questionnaire (demographics, medical history, concomitant medications, etc.) prior to study enrollment. A urinalysis via urine dipstick and pregnancy test (for women of child bearing potential) will be performed at screening. If the urinalysis is positive for leukocytes a urine culture will be sent. Patients with a positive urine culture may be treated per standard of care by the study physician. After treatment is completed, a repeat urine will be checked. If repeat urinalysis is negative, the subject will be allowed to complete the voiding diary and continue with study activities. The diary will be collected and reviewed at the first scheduled treatment visit (within 21 days from screening visit). If the patient meets the eligibility criteria, they will be randomized (1:1) into the sham or accelerated PTNS group.

Our goal is to have patients complete all three treatments within one week (7 days) but as there are always impedances (scheduling conflicts, illness, etc.) we will allow patients to complete all treatments within 2 weeks (14 days) if necessary. Patients will be allowed back-to-back treatments (i.e. two days in a row) if they should elect to do so. Adverse events and concomitant medications will be assessed at each treatment whether sham or active PTNS. GRA will be gathered at each visit beginning with the second induction treatment.

After completing the one-week induction consisting of three active or sham treatments, patients will receive a phone call three days ( $\pm$  1 day) after the last treatment to assess for any adverse events as well as remind them to start filling out their 3 day diary if they have not already begun to do so. This will also serve as a reminder phone call for their upcoming appointment.

One week post-induction ( $\pm$ 3 days), patients will return for an office visit. OAB-q SF, GRA and 3-day voiding diary will be collected. We will also assess for adverse events and concomitant medications at this visit. A blinding assessment questionnaire will be administered as well. A urinalysis will be completed.

At 4, 8, and 12 weeks post-induction ( $\pm$  7 days), patients will return for follow-up appointments. Non-modified OAB-q SF, GRA and 3-day voiding diary will be collected and a urinalysis completed. Maintenance treatments (sham or active PTNS depending on treatment arm) will be given. Maintenance treatment will consist of a 30 minute treatment per standard of care. We will also assess for adverse events and concomitant medications at each of these visits.

After all study activities are complete, patients will be un-blinded at week 12 marking the end of the study. Those who were in the sham arm will be offered the opportunity to continue on to the open label phase of the study. Subjects in the open label phase will be offered the same accelerated treatments as those in the initial active PTNS treatment group. They will have up to 12 weeks to decide if they would like to continue on to the open label phase. This option will also be offered to those who had been previously randomized to the Sham group prior to the protocol amendment, even if they have completed their visit schedule. The follow up schedule will also be conducted in the same manner. Either of the groups can be offered re-induction per insurance requirements if they elect to do so with their

physician or can seek alternative treatments (BTX, sacral neuromodulation, etc.) per standard of care.

Our goal is to have patients complete all three open label treatments within one week (7 days) again, as there are always impedances (scheduling conflicts, illness, etc.) we will allow patients to complete all treatments within 2 weeks (14 days) if necessary. Patients will be allowed back-to-back treatments (i.e. two days in a row) if they should elect to do so. Adverse events and concomitant medications will be assessed at each treatment whether sham or active PTNS. GRA will be gathered at each visit beginning with the second induction treatment.

After completing the one-week open label induction consisting of three active treatments, patients will receive a phone call three days ( $\pm$  1 day) after the last treatment to assess for any adverse events as well as remind them to start filling out their 3 day diary if they have not already begun to do so. This will also serve as a reminder phone call for their upcoming appointment.

One week post- open label induction ( $\pm$ 3 days), patients will return for an office visit. OAB-q SF, GRA and 3-day voiding diary will be collected. We will also assess for adverse events and concomitant medications at this visit. A urinalysis will be completed.

At 4, 8, and 12 weeks post-open label induction ( $\pm$  7 days), patients will return for follow-up appointments. Non-modified OAB-q SF, GRA and 3-day voiding diary will be collected and a urinalysis completed. Maintenance treatments using active treatment will be given. Maintenance treatment will consist of a 30 minute treatment per standard of care. We will also assess for adverse events and concomitant medications at each of these visits.

	Consent and Screening	Week 1: Induction Treatments (Tx)	3 Day Post-Induction Phone Call (± 1 day)	1 Week Post-Induction Visit (± 3 days)	4 Weeks Post-Induction Visit (± 7 days)	8 Weeks Post-Induction Visit (± 7 days)	12 Weeks Post-Induction Visit (± 7 days)	Part 2/Week 1 Induction Treatments (Tx)	Part 2/3 Day post-induction phone call (± 1 day)	Part 2/1 Week post-induction visit (± 3 days)	Part 2/14 Weeks Post-Induction Visit (± 7 days)	Part 2/8 Weeks Post-Induction Visit (± 7 days)	Part 2/12 Weeks Post-Induction Visit (± 7 days)	
Consent	X													
Eligibility	X													
Demographics, medical history	X													
OABq-SF	X							X	X	X	X	X	X	
3-day Voiding Diary	X							X	X	X	X	X	X	
Pregnancy test	X													
Urinalysis	X							X	X	X	X	X	X	
Induction Tx	X								X	X	X	X	X	
Maintenance Treatment								X	X			X	X	
GRA								X	X	X	X	X	X	
Blinding Assessment								X			X			
Concomitant Medications	X							X	X	X	X	X	X	
Adverse events	X							X	X	X	X	X	X	
Case Report Forms/Data Entry/Query Resolution	X							X	X	X	X	X	X	
Un-Blinding										X				

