## V. Eligibility Criteria

### Inclusion criteria:

- Women and men  $\geq$  18 years of age
- Self-reported failed conservative care of behavioral modifications and / or oral medications
- A score of  $\geq$  4 on question 1 of the OAB-q symptom bother short form completed by the patient at screening
- Average urinary frequency of  $\geq$  8 voids per day as recorded on initial 3-day voiding diary
- Self-reported bladder symptoms  $\geq$  3 months
- On a stable dose of antimuscarinics/beta-3 agonists for  $\geq$  4 weeks, and willing to remain on the medication for the duration of the study OR discontinued antimuscarinics/beta-3 agonists for  $\geq$  2 weeks
- Capable of giving informed consent
- Ambulatory and able to use toilet independently without difficulty
- Capable and willing to follow all study-related procedures

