### Exclusion criteria:

- Pregnant or planning to become pregnant during study duration
- Diagnosis of neurogenic bladder
- Botox use in bladder or pelvic floor muscles within past 12 months
- Pacemakers or implantable defibrillators
- Current urinary tract infection
- Active use of neuromodulation in any other form. If patient has InterStim, must be turned off for 2 weeks for a washout period and remain off during the entirety of the study.
- Current use of Transcutaneous Electrical Nerve Stimulation (TENS) in pelvic region, back or legs
- Previous PTNS treatment who received greater than 6 treatments. Those who have received less than 6 treatments will be allowed to screen if the last treatment was at least 6 months prior to screening.
- Use of investigational drug/device therapy within past 4 weeks
- Participation in any clinical investigation involving or impacting gynecologic, urinary or renal function within past 4 weeks
- Current or past history of any physical condition that, in the investigator's opinion, might put the subject at risk or interfere with study results interpretation (i.e. pelvic cancer or pelvic radiation treatment)

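### After a treated screening infection the voiding diary waits for a negative urine but the OAB-q SF need not, so a few entry scores and OABq-SF baselines may date from the infection

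*Combined protocol and SAP*

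**What the plan says.** Section III (Methodology) of the combined protocol and SAP lists the baseline instruments together: "Consented patients will complete the Overactive Bladder Questionnaire Short Form (OAB-q SF), 3-day voiding diary and enrollment questionnaire", all before enrolment. It then sets the infection check: "A urinalysis via urine dipstick and pregnancy test (for women of child bearing potential) will be performed at screening". A dipstick positive for leukocytes leads to a culture, and for a positive culture the text reads "Patients with a positive urine culture may be treated per standard of care by the study physician", followed by "After treatment is completed, a repeat urine will be checked" and then "If repeat urinalysis is negative, the subject will be allowed to complete the voiding diary and continue with study activities". The diary is reviewed at the first scheduled treatment visit, no more than 21 days after the screening visit, and eligible patients are then randomised.

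Section V (Eligibility Criteria) excludes "Current urinary tract infection". Among the inclusion criteria, the bother score of at least 4 is the one given "on question 1 of the OAB-q symptom bother short form completed by the patient at screening". The frequency criterion, at least 8 voids per day, is read from the initial diary.

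Sections II and VI make both the diary variables and the OABq-SF secondary endpoints at one week post-induction, and add an analysis of change from baseline. Neither section says which OAB-q SF is the baseline form.

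**The concern.** Excluding current infection and holding back the diary until the urine is negative both imply that infection can distort bladder symptoms. The same reasoning applies to a symptom-bother questionnaire, yet the safeguard names only the diary. Both instruments decide eligibility and both supply a baseline.

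Two things are at stake for a patient who enters by this route. First, the question 1 criterion may be met on an answer given while infected. Second, the OABq-SF change from baseline may include recovery from the infection as well as any response to stimulation or sham. That patient's two baselines would then describe different states: the questionnaire before clearance and the diary after it.

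**Working it through.** **Order of events for a culture-positive patient, from sections III and V**

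| Step | Voiding diary | OAB-q SF |
|---|---|---|
| Screening, dipstick done | Held if the culture is positive and treated | Question 1 score taken from the form done at screening |
| Treatment, then repeat urine | Still held | No instruction |
| Repeat urinalysis negative | Released for completion | No instruction to complete or repeat |
| First treatment visit, before randomisation | Collected and reviewed | Not mentioned |
| One week post-induction | Collected | Collected |

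After the screening form, the next OAB-q SF named in the text is the one at the one-week post-induction visit. The Schedule of Research Activities has its first OABq-SF mark under Consent and Screening. Its later marks are displaced in the text available here, so I draw nothing from them.

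**The plan's own figure.** The only related figure is the sample size. The pooled-variance Z test, two-sided at 5% with 80% power, uses rates 0.583 and 0.219 and mean 0.401:

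n = [1.960 × √(2 × 0.401 × 0.599) + 0.842 × √(0.583 × 0.417 + 0.219 × 0.781)]² / 0.364² = 27.2, so 28 per arm. Then 28 / 0.90 = 31.1, so 32 per arm and 64 in total, as stated.

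This calculation concerns GRA responders. Neither this point nor its fix changes it.

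**Size under stated assumptions.** The documents give neither the proportion of patients with a positive screening culture nor the SD of the OABq-SF. Let f be the affected proportion and b the worsening of the baseline score due to infection, in units of the SD of change. I assume f = 0.03 to 0.15 (64 × f = about 2 to 10 patients) and b = 0.5 to 1.0.

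- Overstatement of mean within-arm change, f × b: 0.03 × 0.5 = 0.015 SD, up to 0.15 × 1.0 = 0.15 SD.
- Inflation of the SD of change, √(1 + f(1 − f)b²): √(1 + 0.0291 × 0.25) = 1.004, up to √(1 + 0.1275 × 1) = 1.062, that is 0.4% to 6%.
- Expected between-arm difference due to infection: f × b − f × b = 0, because infection at screening precedes 1:1 randomisation.
- SD of the chance between-arm imbalance, b × √(f(1 − f) × 2/32): 0.5 × √(0.0291/16) = 0.02, up to 1.0 × √(0.1275/16) = 0.09 SD. The standard error of a between-arm difference with 32 per arm is √(2/32) = 0.25 SD.

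On a 0–100 scale, assuming instead f = 0.05 to 0.15 and a shift of 10 to 20 points, the within-arm overstatement is 0.05 × 10 = 0.5 to 0.15 × 20 = 3 points. A deliberately uneven split, 4 affected patients in one arm and 1 in the other, gives 3/32 × 10 = 0.9 to 3/32 × 20 = 1.9 points between arms. With an assumed change-score SD of 15 to 25 points, the standard error is 15 × 0.25 = 3.75 to 25 × 0.25 = 6.25. Even that split is therefore between 0.94/6.25 = 0.15 and 1.88/3.75 = 0.5 of a standard error.

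**The case against.** The strongest reply is that the text is loose rather than wrong. The OAB-q SF is to be completed before enrolment, which need not mean the day of the dipstick. Screening can be read as a phase, since randomisation follows all screening activities and up to 21 days may pass before first treatment. The sentence that releases the diary also lets the patient go on with the study generally, which leaves room for a repeat form. No section says that the screening form is the baseline.

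This stands in part. A reader might infer that the protocol forbids a repeat, or fixes an infected score as baseline; it does neither, and both readings rest on silence. But nothing requires a form after clearance, and if one were completed nothing says which form governs entry or serves as baseline. Staff could handle such patients differently.

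The second reply is that eligibility is partly protected. Such a patient must also report at least 3 months of symptoms and failed conservative care, and must record at least 8 voids per day on a diary completed after clearance. That is right. It narrows the route but does not protect the question 1 criterion itself or the OABq-SF baseline.

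The third reply is that the trial's comparisons are between arms, and a disturbance before randomisation falls on both arms alike in expectation. That stands in full. Any imbalance is ordinary chance variation, which the observed variance already reflects.

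**Conclusion.** The gap is real and its consequence is modest. Followed as written, the plan allows a few patients to qualify on, and carry as OABq-SF baseline, a score given during infection, while their diary baseline is taken after clearance. The expected result is some inflation of within-arm OABq-SF change and a little added noise in a secondary change-from-baseline analysis.

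Two stronger conclusions are tempting. One is that the comparison of PTNS with sham is biased; infection at screening precedes randomisation, so no systematic difference is expected. The other is that the primary endpoint is compromised; GRA does not use the OAB-q SF score, and the documents do not show that a patient's recall of an infected state enters it. Repeating the questionnaire would not address that possibility in any case.

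The size cannot be derived from the documents. The range of 0.015 to 0.15 SD within arm depends wholly on the assumed proportion affected and the assumed shift. The procedural gap itself depends on neither.

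**What to change.** In section III, state that a patient treated for a positive culture completes or repeats the OAB-q SF after the negative repeat urinalysis and before randomisation, together with the diary. In section V, state that for such a patient this form decides the question 1 criterion, and that it is the OABq-SF baseline for the change analyses in sections II and VI.

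The cost is a sentence or two of text and one extra short form for a few patients, handed in at the visit where the diary is already collected. There may be a few more screen failures among patients whose score falls below 4 once the infection has cleared. Sample size, significance level and power are unchanged.
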